The rationale for this amendment is to address Subject Expert Committee (SEC) recommendation of revising the Phase IV study protocol to include all indications approved by CDSCO in the Marketing Authorization of Augmentin ES. Therefore, the indication is being revised to Acute Respiratory Tract Infections (ARTIs) i.e. inclusion of CABP and ABRS in addition to AOM

Section # and Name	Description of Change	Brief Rationale
Throughout the protocol	Acute otitis media is replaced with Acute respiratory tract infection.	To broaden the indication and include acute respiratory tract infections. Acute respiratory tract infection meaning addition of CABP and ABRS in addition to AOM.
Section 1.1: Synopsis Section 3: Objectives and Endpoints	Added an additional secondary endpoint of Early clinical response at on-therapy visit (Day 3 to 5). Added tables providing definitions of primary and secondary clinical response.	To assess if there is any clinical response early during the treatment period. To clarify the definitions of different responses as part of clinical response.
Section 1.2: Schema	Changed the study schema.	Updated as per the changed study design.
Section 1.3: Schedule of Activities	Added an additional column for interim visit between OT visit and EOT visit Added a row for radiographic evaluations and the respective foot note Added early clinical response at OT	Updated as per the changed study design.
Section 2.2: Background	Added background information about ARTIs	Since the indication is changed from AOM to ARTIs updated this section to include information about ARTIs.
Section 2.3.1: Risk Assessment	Added the risk of exposure to ionizing radiation from X ray and its mitigation strategy	Since X ray is included at Preliminary Visit (if required as per investigator's discretion), the related risk is included.
Section 4.1: Overall Design	Updated details about OT visit. Added the details of additional interim visit.	Updated as per the changed study design.
Section 5: Study Population	Added inclusion criteria for patient with ABRS and CABP. Updated the exclusion criteria	To include the patients with ABRS and CABP.
Section 5.4: Study Procedures	Updated details of OT visit and added details of the Interim visit	Updated as per the changed study design.

Section # and Name	Description of Change	Brief Rationale
	Added radiological evaluation at preliminary visit	
Section 8.1: Efficacy assessment	Added evaluation of early clinical response at OT visit. Added evaluation of primary clinical response at Interim visit.	Updated as per the changed study design.
Section 8.2: Safety Assessment	Added section on Radiographic Evaluations (Section 8.2.4)	To include information about the X ray.
Section 1.1: Synopsis Section 9.2: Sample Size Determination	Sample size is changed from 200 to 270 (without dropouts) and 310 (including dropouts)	Sample size is changed to accommodate the patients with ABRS and CABP along with the AOM patients.
Section 9.4.3: Secondary Endpoint	Added details on estimand	Update estimand strategy
Section 9.2:	A new subsection (Section 9.2.1: Sample Size Sensitivity) is added	To provide details regarding the calculation of the precision of sample size
Appendix 3	Added radiographic evaluations along with the Laboratory evaluations	To include information about the X ray.

TABLE OF CONTENTS

	PAGE
PROTOCOL AMENDMENT SUMMARY OF CHANGES TABLE	3
1. PROTOCOL SUMMARY	10
1.1. Synopsis	10
1.2. Schema	15
1.3. Schedule of Activities (SoA).....	17
2. INTRODUCTION.....	20
2.1. Study Rationale	20
2.2. Background	21
2.3. Benefit/Risk Assessment	23
2.3.1. Risk Assessment	23
2.3.2. Benefit Assessment	28
2.3.3. Overall Benefit: Risk Conclusion	28
3. OBJECTIVES AND ENDPOINTS	28
4. STUDY DESIGN	30
4.1. Overall Design	30
4.2. Scientific Rationale for Study Design	32
4.2.1. Participant Input into Design	33
4.3. Justification for Dose	33
4.4. End of Study Definition	33
5. STUDY POPULATION	34
5.1. Inclusion Criteria	34
5.2. Exclusion Criteria.....	36
5.3. Lifestyle modifications.....	37
5.4. Study Procedure	37
5.4.1. Schedule of Assessments.....	37
5.4.2. Screening, Enrolment and Baseline Assessments	37
5.4.3. On Therapy.....	38
5.4.3.1. Day 1	38
5.4.3.2. On-therapy Visit (Days 3 to 5)	38
5.4.3.3. Interim Visit (Within 24 Hours of Notification).....	39
5.4.4. End of Therapy Visit (Day 12 to 14)	39
5.4.5. Post Therapy	40
5.4.5.1. Interim Visit (Day 15 to 21)	40
5.4.5.2. Follow up Visit (Day 22-28).....	40
5.4.6. Reason of Concluding Study.....	41
5.5. Screen Failures.....	41
6. STUDY INTERVENTION.....	42
6.1. Study Intervention(s) Administered	42
6.1.1. Medical Devices.....	43
6.2. Preparation/Handling/Storage/Accountability	43
6.3. Measures to Minimize Bias: Randomization and Blinding	44
6.4. Study Intervention Compliance	44
6.5. Concomitant Therapy.....	45

6.5.1. Rescue Medicine	45
6.6. Dose Modification	45

1. PROTOCOL SUMMARY

1.1. Synopsis

Protocol Title: A Multicentre, Open-label, Non-comparative Phase IV Clinical Study to Evaluate the Safety and Clinical Efficacy of Augmentin Extra Strength (ES)-600 (amoxicillin/potassium clavulanate 14:1 combination) in Children with Acute Respiratory Tract Infections (ARTIs) in India.

Short Title: A Phase IV Study to Evaluate the Safety and Efficacy of Augmentin Extra Strength (ES)-600 (amoxicillin/potassium clavulanate 14:1 combination) in Children with Acute Respiratory Tract Infections (ARTIs) in India.

Rationale: Augmentin (ES)-600 is a high-dose amoxicillin/clavulanic acid (AMC/CVA) 14:1 formulation that allows administration at 90/6.4 mg/kg/day in two divided doses, ie, double the previously recommended standard amoxicillin dosage (45 mg/kg/day) without doubling the unit dose of potassium clavulanate in a fixed dose combination formulation, inhibitory activity of CVA against bacterial beta-lactamases is maintained. Optimizing the PK/PD (ie, $T > MIC$ values) of Augmentin (ES)-600 maximizes bacterial eradication such as *Streptococcus pneumoniae* (including penicillin-resistant *S. pneumoniae* (PRSP); MIC 2-4 ug/mL), *Haemophilus influenzae* (*H. influenzae*) and *Moraxella catarrhalis* (*M. catarrhalis*); principal respiratory pathogens implicated in acute respiratory tract infections (ARTIs) in children. This assures the highest probability of clinical cure and reduce the spread and development of resistance.

The safety profile of AMC/CVA is also well understood. Clinical and post marketing surveillance data has also shown favourable results across all AMC/CVA paediatric and adult formulations. Most adverse events are mild and transient. The most commonly occurring events reported in children are mild transient gastrointestinal effects.

Due to non-availability of Augmentin (ES)-600 in India, most physicians can only use available standard Augmentin 7:1 (45/6.4 mg/kg/day) formulation and double the dose to achieve the guideline recommended higher dose of amoxicillin at 90 mg/kg/day in ARTIs like AOM. However, doubling the dosage using 7:1 formulation causes unnecessary exposure to higher proportionate dose of CVA (12.8 mg/kg/day) as a unit dose of 6.4 mg/kg/day of CVA is only required for efficacy against beta-lactamase producing respiratory pathogens like *H. influenzae* and *M. catarrhalis*. Hence, there is an unmet need for availability of Augmentin (ES)-600 in India.

In this regard, the Indian Regulatory Agency (CDSCO) has granted a marketing authorization on 08 June 2020 for import/marketing of Augmentin (ES)-600 in India to the Sponsor (GlaxoSmithKline), with a post marketing commitment to conduct a

Phase IV study in India, whose purpose is to generate safety data on Augmentin (ES)-600 in paediatric population in India.

To this effect, the current study is designed to assess the safety and clinical efficacy of Augmentin (ES)-600, AMC/CVA (14:1) at 90/6.4 mg/kg/day in two divided doses every 12 hours in children (age between 6 months and 12 years) with ARTIs, including acute otitis media (AOM), acute bacterial rhinosinusitis (ABRS) and community acquired bacterial pneumonia (CABP).

The purpose of this study is to confirm the safety and clinical efficacy profile of Augmentin (ES)-600 in paediatric population in India.

Objectives and Endpoints:

The following are the objectives and endpoints of the study:

Objectives	Endpoints
Primary	Primary

 The primary objective of the study is to assess treatment-emergent adverse events (TEAEs) in children receiving Augmentin (ES)-600 (AMC/CVA 14:1) at 90/6.4 mg/kg/day in two divided doses, administered for 10 days in ARTIs (AOM, ABRS or CABP). 	
 Safety will be evaluated by assessing the incidences of treatment emergent adverse events (TEAE).[§]
Secondary	
 The secondary objective of the study is to assess clinical efficacy and incidence of protocol defined diarrhoea (PDD)** in children receiving Augmentin (ES)-600 (AMC/CVA 14:1) at 90/6.4 mg/kg/day in two divided doses administered for 10 days in ARTIs (AOM, ABRS or CABP). 
 Efficacy assessment* will be based on: 
 Early clinical response at on-therapy visit (Day 3 to 5), defined in terms of 'success' or 'failure' to study intervention Primary clinical response at the end-of-therapy visit (Day 12 to 14), defined in terms of 'success' or 'failure' to study intervention Secondary clinical response at follow-up (Day 22 to 28) ie, 'success' or 'failure'.

Objectives	Endpoints
	
 Incidence of protocol-defined diarrhoea (PDD)** in children receiving Augmentin (ES)-600 (AMC/CVA 14:1) at 90/6.4 mg/kg/day in two divided doses administered for 10 days in ARTIs (AOM, ABRS or CABP).

[§]A treatment-emergent adverse effect (TEAE) is defined as an AE which has its onset date on or after treatment start date and on or before treatment stop date + 1 day. All adverse events (AEs) experienced during the same period will be monitored. The detail is described in Section 8.3: “Adverse Events and Serious Adverse Events”.

**Protocol-defined diarrhoea is:

- 3 or more watery stools in one day OR
- 4 or more loose/watery stools in one day OR
- 2 watery stools per day for two consecutive days OR
- 3 loose/watery stools per day for two consecutive days.

*Efficacy assessment will be made using following criteria:

- Early or Primary Clinical Response**

Success	Clinical cure	Sufficient resolution or improvement of the signs and symptoms. No additional antibiotic therapy is indicated.
	Improvement	Improvement in at least 1 presenting sign/symptoms. No additional antibiotic indicated.
Failure	Clinical failure	Non-improvement or deterioration in any sign/symptoms after 2 or more days of therapy. Additional antibiotic therapy is indicated.
	Unable to determine	A valid assessment of clinical outcome could not be made (eg, participant did not attend or consent to clinical examination or lost to follow-up).

- Secondary Clinical Response**

Success	Persistent clinical cure*	Sufficient resolution of signs/symptoms for those participants who were clinically cured or improved at the end of therapy. No additional antibiotic indicated.
Failure	Clinical recurrence	Reappearance of signs/symptoms for those participants who were clinically cured or improved at the end of therapy. Additional antibiotic therapy is indicated.

	Unable to determine	A valid assessment of clinical outcome could not be made (eg, participant did not attend end of therapy visit, or extenuating circumstances or lost to follow-up).
--	---------------------	--

* Participants who showed 'improvement' at EOT (ie, clinical 'success') and remained same at FU without requiring additional intervention, will be categorized as 'persistent clinical cure'.

Overall Design:

This study is an open label, multicentre, non-comparative study. Participants will be children aged between 6 months to 12 years, presenting with ARTIs, including AOM, ABRS or CABP.

At Preliminary Visit (Day 0) after signing the informed consent form by the parent/guardian and assent form by children between 7 to 12 years of age, a series of screening evaluations will be performed including laboratory and radiographic evaluations, in order to determine whether prospective study participant meets the inclusion criteria. Enrolled participants will receive supervised first dose of study intervention from participant pack, after demonstration of medication reconstitution procedure. In case first dose can be given on Day 0 (after availability of laboratory test result and radiological evaluation [Only if needed by investigator's discretion]), the same will be considered as Day 1. All participants will receive Augmentin (ES)-600 at 90/6.4 mg/kg/day administered in two divided doses, every 12 hours with food for 10 days.

The incidence of protocol-defined diarrhoea will be determined from information collected from the Patient Diary cards, which will be appropriately translated for all languages required based on sites participating in the trial. Protocol-defined diarrhoea is:

- 3 or more watery stools in one day OR
- 4 or more loose/watery stools in one day OR
- 2 watery stools per day for two consecutive days OR
- 3 loose/watery stools per day for two consecutive days.

After a minimum of two treatment days (four doses) of study intervention has been taken, an 'on-therapy' (OT) visit will be scheduled between Day 3 and 5.

During this visit, the Investigator/study coordinator shall assess safety (primary endpoint) and 'early clinical response' (secondary endpoint). Safety parameter includes treatment-emergent adverse events (TEAEs) for primary study objective. Additionally, clinical status, study intervention compliance, completion of Patient Diary cards, and use of concomitant medications will also be assessed. The Investigator will assess safety parameters and clinical status whereas study coordinator will check other parameters with coordinated effort.

Participants with worsening of signs and symptoms, severe AE, SAE, or having PDD at OT visit (Day 3 to 5) will be assessed by investigators and withdrawn from study as per investigator's discretion and treated appropriately. In such case, the OT visit will be considered as End of Therapy (EOT), and all evaluations that are planned at scheduled EOT (Day 12 to 14) will be completed at this visit. However, these participants will return at Follow-Up (FU) visit (Day 22 to 28) for safety assessment.

Participants with worsening of signs and symptoms, severe AE, SAE, or having PDD after OT visit (Day 3 to 5) but prior to EOT visit will be assessed by investigators and withdrawn from study as per investigator's discretion and treated appropriately. In such case, the interim visit will be considered as EOT visit, and all evaluations that are planned at scheduled EOT (Day 12 to 14) will be completed in this visit. However, these participants will return at FU visit (Day 22 to 28) for safety assessment.

The participants continuing in the study will return for the scheduled EOT evaluation between Day 12 and 14. The Investigator will enquire the participant or parent/legal guardian about development of AEs and use of concomitant medication(s). The Investigator will perform safety (primary endpoint) and primary clinical response (secondary endpoint) evaluation. Patient Diary cards and unused medication will be returned at this visit.

Participants who experience recurrence of signs/symptoms or any new AEs *after* EOT visit (Day 12 to 14), but prior to scheduled FU visit (Day 22 to 28) will be required to visit the study site twice post EOT - once for the interim visit at the time of any recurrence (Day 15 to 21) and for the scheduled FU visit (Day 22 to 28). At the interim visit, all the evaluations which are to be performed at scheduled FU visit will be conducted. However, in such cases, all evaluations except secondary clinical response evaluation will be repeated at scheduled FU visit (Day 22 to 28). All participants experiencing recurrence post EOT will be treated according to the Investigator's discretion.

All participants, including withdrawals or clinical "failures" at EOT or had disease recurrence after EOT, will return for scheduled FU visit on Day 22 to 28. This visit is required for safety assessment and administration of additional medication, if warranted.

The participants continuing in the study will return for the scheduled FU visit between Day 22 and 28. The visit be considered as 'end of study' visit, where the Investigator will perform final safety (primary endpoint) and secondary clinical response (secondary endpoint) evaluation (except for recurrence) during the visit.

In general, FU visit at Day 22 to 28 includes both safety and efficacy assessment for participants who were clinical "success" at EOT, but only safety assessment for the

participants who were clinical “failures” at EOT or had disease recurrence after EOT. These participants are, by definition, clinical failures at follow-up visit.

Disclosure Statement: This is a single group open-label treatment study in ARTI in children (age 6 months to 12 years).

[figure not shown]
Number of Participants: A total of 310 subjects will be enrolled and dosed.

Note: "Enrolled" means a participant's, or their legally acceptable representative's, agreement to participate in a clinical study following completion of the informed consent process.

Intervention Groups and Duration: The current study is a single arm, open label, non-comparative study. Eligible participants will receive Augmentin (ES)-600 [AMC/CVA 14:1] at 90/6.4 mg/kg/day administered in two divided doses, every 12 hours with food for 10 days.

Data Monitoring or Other Committee: Not Applicable.

1.2. Schema

- Abbreviations: AE=Adverse event; ECR=Early Clinical Response; PCR=Primary Clinical Response; SAE = Serious Adverse Event, SCR=Secondary Clinical Response.
- Safety parameter is TEAE (All visits). Efficacy parameter includes ECR (OT visit), PCR (EOT visit), SCR (FU visit) categorized as clinical 'success' or 'failure' as defined in Section 8.1
- Visit 1 can be completed on the same day as the preliminary Day 0 visit if the laboratory test results and radiological assessment (Only if needed by investigator's discretion) are available on the same day.
- Participants with clinical 'failure' or having PDD or severe AE or SAE **at OT visit** (Day 3 to 5), will be withdrawn from the study intervention and treated appropriately (as per Investigator discretion). In such case, the OT visit will be considered as EOT, and all evaluations that are planned at scheduled EOT (Day 12 to 14) will be completed in this visit. However, these participants will return at FU visit (Day 22 to 28) for safety assessment.
- Participants with clinical 'failure' or having PDD or severe AE or SAE **after OT visit** (Day 3 to 5) but prior to EOT, will be scheduled to return to the site for an interim evaluation, within 24 hours of notification to the Investigator. Subjects will then be withdrawn from the study intervention and treated appropriately (as per Investigator discretion). In such case, the interim visit will be considered as EOT visit, and all evaluations that are planned at

scheduled EOT (Day 12 to 14) will be completed in this visit. However, these participants will return at FU visit (Day 22 to 28) for safety assessment.

- f. Participants who experience recurrence of signs/symptoms after EOT visit (Day 12 to 14), but prior to scheduled FU visit (Day 22 to 28) will be required to visit the study site twice post EOT - once during interim visit at the time of any recurrence (Day 15 to 21) and at scheduled FU visit (Day 22 to 28). At this interim visit, all the evaluations which are to be performed at scheduled FU visit will be conducted. However, in such cases, all evaluations except secondary clinical response will be repeated at scheduled FU visit (Day 22 to 28). All participants experiencing recurrence post EOT will be treated according to the Investigator's discretion.

1.3. Schedule of Activities (SoA)

Assessments	Preliminary Visit	Visit 1*	On-therapy Visit ^a (OT)	Interim Visit ^b ('Failure' or AE)	End of Therapy Visit ^c (EOT)	Interim Visit ^d (Recurrence)	Follow up Visit ^e (FU)
Days**	Day 0*	Day 1	Days 3 to 5	Within 24 hours	Day 12 to 14	Day 15 to 21***	Day 22 to 28
Written dated informed consent	X****						
Inclusion/exclusion	X						
Medical history	X						
Demographics	X						
Vital signs ^f	X		X	X	X	X	X
Physical examination ^g	X		X	X	X	X	X
Laboratory evaluations ^h	X						
Radiographic evaluations ⁱ	X						
Prior/concomitant medication	X		X	X	X	X	X
Bowel movements	X		X	X	X	X	X
Local examination ^j	X		X	X	X	X	X
Clinical assessment ^k	X		X	X	X	X	X

Assessments	Preliminary Visit	Visit 1*	On-therapy Visit ^a (OT)	Interim Visit ^b ('Failure' or AE)	End of Therapy Visit ^c (EOT)	Interim Visit ^d (Recurrence)	Follow up Visit ^e (FU)
Baseline signs and symptoms ^f	X						
Dispensing of study intervention		X					
Dispensing of Patient Diary card ^m		X					
Adverse events ⁿ		X	X	X	X	X	X
Early clinical response			X				
Primary clinical response				X	X		
Secondary clinical response						X	X ^o
Protocol-defined Diarrhoea ^p			X	X	X	X	X
Return of remaining study intervention				X	X		
Collection of Patient Diary card				X	X		
Review of Patient Diary card			X	X	X		
Assessment of compliance				X ^q	X ^q		
Study conclusion							X

^a Scheduled OT (Safety and early clinical response). If clinical 'failure' or PDD or severe AE/SAE at OT, participant will be withdrawn and treated appropriately. In such case, OT visit will be considered as EOT visit.

^b Interim visit (< 24 hrs of notification). Only if clinical ‘failure’ or having PDD or severe AE or SAE occurring after OT visit (Day 3 to 5) but prior to EOT.

^c Primary clinical response at EOT.

^d Required only if ‘recurrence’ occurs between EOT and FU.

^e Safety and clinical response at follow up.

^f Vital signs include body temperature, pulse rate, and respiratory rate.

^g Physical examination will include, measurement of height and weight, assessments of the skin, cardiovascular, respiratory, gastrointestinal and neurological systems.

^h Laboratory evaluations include hematology, plasma creatinine, aspartate aminotransferase (AST), alanine aminotransferase (ALT) and bilirubin.

ⁱ Radiographic evaluation will include Chest X ray and X ray of nasal/paranasal sinus (performed for patients presumed to have CABP and ABRS) as per investigators discretion.

^j Local examination refers to ear, nose/paranasal sinus or chest examination depending upon the primary diagnosis ie, AOM, ABRS or CABP

^k Includes assessment of disease at baseline and evaluation of clinical improvement or deterioration at other visits during study, as per Investigator’s discretion.

^l Includes baseline signs and symptoms (other than disease under study).

^m The parent/legal guardian should record the AEs, dosing information, diarrhoea related information in the Dairy Card through the treatment period and until EOT. Patient Diary cards will be appropriately translated for all languages required based on sites participating in the trial.

ⁿ All AEs will be collected from the signing of the ICF until the follow-up visit at the time points specified.

^o The secondary clinical response evaluation will be performed at scheduled FU visit only for participants who were treatment successes at the EOT. This is unlike participants with disease recurrence post EOT, whose secondary clinical response evaluation would have already taken place at interim visit, at the time of recurrence.

^p Incidence of protocol-defined diarrhoea will be assessed (as a secondary endpoint) at EOT (Day 12 to 14), scheduled FU visit (Days 22 to 28) and interim visit, if any.

^q Not required for the participants who were withdrawn from the study intervention due to worsening, or no improvement, or requirement of additional antibiotics during OT visit (Day 3 to 5).

*In case first dose can be given on Day 0 (after laboratory test result availability), the same will be considered as Day 1.

**Rationale for range: Days 3 to 5; 12 to 14; 15 to 21, and 22 to 28: Basis previous GSK studies. Day 15 to 21 is to cover interim period between EOT and FU to factor any disease recurrence. Refer to Section 5.4 for the details of the evaluation to be performed at each visit.

*** Participants with disease recurrence following the EOT visit (Day 12 to 14), but prior to the scheduled FU visit (Day 22 to 28) will be required to visit the study site twice - once during interim visit at time of recurrence (Day 15 to 21) and again at scheduled FU visit (Day 22 to 28). At interim visit all the evaluations which are to be performed at scheduled FU visit, including primary and secondary endpoint assessments will be performed. However, at scheduled FU visit (Day 22 to 28), all evaluations conducted at interim visit will be repeated, except secondary clinical response.

**** Informed consent to be taken from by the parent/guardian and assent from children between 7 to 12 years.

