5.4.3. On Therapy

5.4.3.1. Day 1

- On Day 1 of the treatment period, the parent/guardian of the participant will be provided with the following:
 - Study intervention
 - Patient Diary card
- The parent(s)/legal guardian(s) of the participant will be instructed about study intervention reconstitution, dosing, storage and entering the details in the Patient Diary card. The first dose will be from the participant pack.
- Any adverse events after signing the informed consent form will be collected.

Note: Visit 1 can be completed on the same day as the preliminary day 0 visit if the laboratory test results are available on the same day.

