8.3.1. Time Period and Frequency for Collecting AE and SAE Information

- All SAEs will be collected from the signing of the informed consent form until the follow-up visit at the time points specified in the SoA (Section [1.3](#)).
- All AEs will be collected from the start of study intervention until the follow-up visit at the time points specified in the SoA (Section [1.3](#)).

- Medical occurrences that begin before the start of study intervention but after obtaining informed consent will be recorded on the Medical History/Current Medical Conditions section of the case report form (eCRF) not the AE section.
- All SAEs will be recorded and reported to the Sponsor or designee immediately and under no circumstance should this exceed 24 hours, as indicated in [Appendix 3](#). The Investigator will submit any updated SAE data to the Sponsor within 24 hours of it being available.
- Investigators are not obligated to actively seek AEs or SAEs after the conclusion of the study participation. However, if the Investigator learns of any SAE, including a death, at any time after a participant has been discharged from the study, and he/she considers the event to be reasonably related to the study intervention or study participation, the Investigator must promptly notify the Sponsor.

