#### Treatment Emergent Adverse Event:

An AE will be defined as Treatment emergent adverse event (TEAE) if the AE start date is on or after treatment start date & on or before treatment stop date +1

Study Treatment Start Date ≤ AE Start Date ≤ Study Treatment Stop Date +1

If the last dose of study drug is missing and the AE start date is on or after the first dose of study drug, then the AE will be considered as TEAE

If the AE start date is missing or partial then the AE will be considered TEAE unless there is evidence to the contrary (e.g. month/year of onset date is present and is earlier than the month/year of first dose of study medication).

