#### 16.1.1. TEAES: PRIMARY SAFETY ENDPOINT

AEs occurring from when a subject sign informed consent to when a subject exits the study will be accounted for in the reporting. AEs occurring pre-treatment, treatment emergent adverse event (on-treatment) and post-treatment periods will be summarized and listed for the ITT population. A treatment -emergent adverse event is defined as any adverse event that develops after initiation of the study treatments or any adverse event already present that worsens following exposure to study treatment.

The primary safety endpoint will be summarized with counts and percentage of subjects reporting any TEAEs and subjects with at least one or any TEAE with corresponding 95% CI using exact binomial method

The following summaries will be generated for adverse events:

- Adverse event overview by period
- Adverse event overview by period for acute otitis media (AOM)
- Adverse event overview by period for acute bacterial rhinosinusitis (ABRS)
- Adverse event overview by period for community acquired bacterial pneumonia (CABP)
- Treatment emergent adverse events by system organ class, preferred term, overall and indication
- Adverse events by system organ class, preferred term, overall and indication - post-treatment
- Common ( $\geq 1\%$ ) treatment emergent adverse events by preferred term, overall and indication
- Common ( $\geq 1\%$ ) adverse events by preferred term, overall and indication - post-treatment

AEs and TEAEs will be sorted by descending order of system organ class (SOC) and total frequency of preferred term (PT) within each system organ class (SOC).

AEs and TEAEs related to study drug will be presented in decreasing order of preferred term (PT). Subjects listing of adverse events by indication (TEAE and post-treatment period) will be produced.

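### AE collection starts at consent in some sections and at first dose in others, and the SAP has two TEAE definitions, so a pre-dose event on the dosing day can enter the primary endpoint

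*Protocol*

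**What the plan says.** **Start of collection**

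- Protocol 1.3, SoA footnote n: "All AEs will be collected from the signing of the ICF until the follow-up visit".
- Protocol 5.4.3.1 (Day 1): "Any adverse events after signing the informed consent form will be collected".
- SAP 16.1.1: "AEs occurring from when a subject sign informed consent to when a subject exits the study will be accounted for in the reporting". The same section plans summaries of pre-treatment AEs.
- Protocol 8.3.1, non-serious events: "All AEs will be collected from the start of study intervention until the follow-up visit". Earlier events go elsewhere: "Medical occurrences that begin before the start of study intervention but after obtaining informed consent will be recorded on the Medical History/Current Medical Conditions section". Such events are expressly kept off the AE pages.
- Protocol 8.3.1, serious events: "All SAEs will be collected from the signing of the informed consent form until the follow-up visit".
- The AE row of the SoA table is first marked at Visit 1, not at the Preliminary Visit.
- SAP 2.2 names only SAEs when it refers to the pre-treatment period.

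**Same-day dosing**

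The SoA allows consent, screening and first dose on one date: "In case first dose can be given on Day 0 (after laboratory test result availability), the same will be considered as Day 1".

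**TEAE definition**

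- SAP 6.4: "Study Treatment Start Date ≤ AE Start Date ≤ Study Treatment Stop Date +1". The protocol's own definition is also date-based and includes the start date.
- SAP 16.1.1 words it differently: the event must arise once treatment has begun, or be an existing event that worsens after exposure. It gives no algorithm.

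SAP 3.3 reports no change in analysis from the protocol.

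**The concern.** The primary endpoint is the percentage of children with at least one TEAE, in a single-arm study with no control rate that would reveal misclassification. An event that precedes all exposure is not treatment-emergent. Whether such an event reaches the AE dataset depends on which section a site follows. Whether it then counts depends on which SAP definition the programmer follows. Neither should be left open for a primary endpoint. A larger sample would not remove the error, and if the order of event and dose is not recorded it may not be recoverable later.

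**Working it through.** **1. The rules applied to one event.** A child consents, has a non-serious event, and takes the first dose later on the same date.

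| Site follows | Where the event is recorded | SAP 6.4 | SAP 16.1.1 |
|---|---|---|---|
| SoA footnote n or 5.4.3.1 | AE page | TEAE | Not a TEAE unless it worsens after dosing |
| Protocol 8.3.1 | Medical History | Not in AE data | Not in AE data |

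The 6.4 result follows from its inequalities. The AE start date equals the treatment start date, so the pre-treatment test (AE date < start date) is false and the TEAE test (start date ≤ AE date) is true. SAP 6.4 also ends the pre-treatment period on the day before first dose. For a child dosed on the Preliminary Visit date, that period ends before it begins, so no event can be pre-treatment. Same-day dosing widens the window but is not essential: an event on the morning of a later Day 1, before the dose, is treated the same way.

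For an SAE, collection starts at consent even under 8.3.1, so the AE-page route is open at every site if the child is then dosed.

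**2. The plan's precision.** Inputs from protocol 9.2: p = 0.379, n = 310. The Wald half-width is 1.96 × √(0.379 × 0.621 / 310) = 5.40 points, giving 32.5% to 43.3%. The plan states 5.43 points and the same interval. A t-quantile with n − 1 = 309 in the denominator gives 5.43. The figure is reproduced closely enough to serve as a yardstick.

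**3. Effect per child.** Each child counted only because of a pre-dose event adds 1/310 = 0.32 points.

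**4. How many children.** The documents do not say. Assumptions, none of them from the documents: the 37.9% rate arises at a constant daily hazard over 11 days (10 treatment days plus the 1-day lag), the same hazard applies before dosing, all sites record from consent, and a share s of children is dosed on the day of consent.

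- Daily hazard: h = −ln(0.621)/11 = 0.476/11 = 0.0433.
- Probability of any event in a gap of g hours: 1 − exp(−h × g/24).
- Probability that it is the child's only countable event: multiply by 0.621.
- Inflation in points: s times that last probability.

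| Gap | Any pre-dose event | Only such an event | Inflation, s = 50% | Inflation, s = 100% |
|---|---|---|---|---|
| 2 h | 0.36% | 0.22% | 0.11 | 0.22 |
| 4 h | 0.72% | 0.45% | 0.22 | 0.45 |
| 8 h | 1.43% | 0.89% | 0.45 | 0.89 |

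At 4 hours this is 310 × 0.5 × 0.0045 = 0.7 to 310 × 1.0 × 0.0045 = 1.4 children.

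**5. What a larger effect would need.** For 3% of children to have only a pre-dose event, 3%/0.621 = 4.8% must have any. That requires a gap of −ln(1 − 0.048)/0.0433 × 24 ≈ 27 hours, which is more than one calendar date.

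**The case against.** Much of the text already agrees with 8.3.1, which is the section dedicated to collection. Footnote n refers to the specified time points, and those begin at Visit 1. Apart from the planned overview-by-period tables, the SAP's pre-treatment output is a listing of SAEs. Expected symptoms of the infection are not AEs under Appendix 3. The study is descriptive with no hypothesis, and an inclusive rule can only over-count harm, not hide it. The eCRF is not among the documents; it may already capture onset time, and SAP Appendix 1 provides formats for times.

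Most of this stands, and it limits the size and severity of the point. It does not remove the conflict. A mark at Visit 1 says when the question is asked, not how far back it reaches, and 5.4.3.1 tells sites at that visit to reach back to consent. Even if onset time is captured, 6.4 does not use it.

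Three stronger readings are tempting, and the documents do not support them:

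- *TEAEs are classified by date alone.* This is true of the protocol definition and SAP 6.4, but not of SAP 16.1.1. The defect is two definitions in one SAP.
- *A same-day SAE before the first dose is always treatment-emergent.* The child must still be dosed to enter the ITT population, and the Medical History bullet in 8.3.1 makes no exception for SAEs. It can happen, but it need not.
- *The inflation could reach 3 points.* Nothing in the documents supports that many pre-dose events, and step 5 shows that it does not fit the plan's own 37.9% rate. A cluster of reactions to screening procedures could raise the figure, but none is documented.

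**Conclusion.** The point holds as a contradiction in how the primary endpoint is collected and defined, with a small numerical consequence. Under SAP 6.4, a pre-dose event recorded as an AE on the first-dose date is counted. For non-serious events this arises at sites that follow footnote n or 5.4.3.1; for SAEs it can arise at any site if the child is then dosed.

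The direction is upward only. The firm figure is 0.32 points per affected child. The total of about 0.2–0.45 points is illustrative and rests on the constant-hazard, 4-hour and 50–100% same-day assumptions, with every site recording from consent. It is lower if some sites follow 8.3.1. Either way it is well inside the stated half-width of 5.43. The case for correcting it rests on clarity and low cost, not on a threat to the study's conclusion.

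**What to change.** **Collection**

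- Align SoA footnote n, protocol 5.4.3.1 and SAP 16.1.1 with protocol 8.3.1: SAEs from consent, other AEs from first dose.
- State in 8.3.1 that the Medical History bullet does not apply to SAEs.
- Limit the SAP's pre-treatment summaries, including the overview-by-period tables, to SAEs.

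**Definition**

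- Use one TEAE definition in SAP 6.4 and 16.1.1, and say how worsening of an existing event is handled.
- For events dated on the first-dose day, exclude those with onset before the first dose. Use onset time if the eCRF captures it; otherwise add a before/after-first-dose tick.
- Count events of unknown order as TEAEs, so that missing information does not lower the estimate.
- Carry the refinement into the protocol definition or record it in SAP 3.3, which now reports no change.

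**Cost.** Wording corrections in both documents, a few lines of programming, and possibly one extra eCRF item for sites to complete. The sample size and visit schedule do not change.
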